5 STUDY INTERVENTION

5.1 Rationale for Promotion of Specific Emollients

Studies in both healthy and diseased skin have shown that most oil-in-water emollients improve skin barrier function by providing the skin a protective lipid barrier.⁵⁵⁻⁶⁴ A wealth of data show petrolatum-based emollients applied to the skin improve barrier function (TEWL and hydration), decreases the effects of skin irritants, and improve clinical outcomes.^{23,65-72} While initial studies found emollient formulations with ceramides and specific lipid ratios improve the skin barrier in mice,⁷³ studies in humans have failed to demonstrate they are superior to simple petrolatum-based emollients.^{23,70,74} A recent clinical study in children found a ceramide-dominant emollient did not provide superior clinical results when compared to Aquaphor (41% petrolatum).²³ Similar findings were found in a clinical study of hand eczema.⁷⁵ Given the lack of data supporting their use over low-cost alternatives, we have primarily included simple petrolatum-based emollients in the study.

Consistent with a pragmatic trial approach, parents will be allowed to select an emollient from a list of five emollients. We performed a survey of pediatric dermatologists (n=10) with a special interest in AD research, who confirmed that the emollients chosen for this trial are ones they found most effective in practice to prevent disease recurrence and that no one emollient is clinically superior. Emollients included in the trial:

1. Are petrolatum-based
2. Are widely available
3. Are of reasonable cost for daily use for 24 months
4. Parents will also be instructed that they can change emollients at any point during study participation, as long as they change to an emollient on the approved list.

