5.2 Emollient Choices

During enrollment procedures, parents assigned to the intervention arm will be instructed to choose an emollient from a study-approved list. They will be instructed to apply full-body emollient once per day on their infant. The emollients that will be recommended for use are shown in Table 3.

Table 3. Emollient Acquisition

| Emollient | Evidence supporting use |
|--|----------------------------------|
| CeraVe ointment (replacement for Aquaphor*) | Refs. 56, 58 |
| Petrolatum (e.g. Vaseline) | Refs. 68, 71 |
| Cetaphil Cream | Ref. 63 |
| CeraVe Cream | Ref. 64 |
| Vanicream | none, pediatric derm recommended |

* CeraVe Ointment contains similar percent petrolatum as Aquaphor (46.5% versus 41%) and does not contain lanolin and bisabolol, two potential sensitizers.

We have received donations from all three sponsor companies to supply emollient options that will be provided to participants. Emollients will be provided directly to the DCC. Other emollients will be acquired using available research funds from the Department of Dermatology, if needed.

After completing the enrollment questionnaire, participants in the intervention arm will receive an e-mail with a survey link to select an emollient from the approved list, followed by a reminder SMS text message to check their e-mail if emollient is not selected. The dyad will be assigned CeraVe cream, the most popular emollient, if one is not selected within three business days of enrollment. Participants in the intervention arm will receive a six-month supply of emollient at enrollment, 6 months, 12 months, and 18 months. Dyads can request additional emollient supplies between scheduled shipments, and those requests will be entered into the study database for use in adherence monitoring.

IRB approval will be accomplished through IND and IDE as outlined from communication with the FDA (See Protocol Appendix G).

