It is possible that farm animal contact will be collinear with other pets (babies with contact with farm animals may usually also have contact with both cats and dogs). In that case, the design variables may be coded as cats and dogs exclusive of farm animals.

Because dogs, and pets in general, are protective, the treatment effect should be greater in families without pets, and/or with cats relative to dogs and other pets.

4. Treatment effect of **CeraVe** cream or ointment (at any time) vs all other emollients in the treatment arm vs controls. A study published since the start of this trial suggests that previously observed benefits from regular emollient use may be attributable to ceramides. Ceramides are present in both CeraVe cream and ointment, which is among the choices for study treatments. Although we are not powered to detect a significant difference from ceramide-containing emollients versus others, we plan to investigate whether use of these products is associated with a reduction in AD. The planned design variables for this analysis are for ceramides (1=CeraVe cream or ointment, 0=otherwise) and other emollients in the treatment arm (1=used, 0=not used). Controls will be used as the reference group.
5. The **baby's age at randomization** may moderate treatment effects, in that emollient use may be most protective if initiated early. Depending on the distribution of ages, this variable will be evaluated as age in days, or if needed, as a categorical variable for early vs late recruitment.
6. More **frequent bathing** may affect the skin barrier and change the treatment effect. Enhance because frequent bathers have more skin barrier damage. Reduce effect because emollient is not potent enough to overcome frequent bathing damage. Frequency of bathing is reported in days per week. This may be analysed as an ordinal variable or as a binary variable with the split determined by existing evidence.

7. **Caesarean birth** may affect the skin microbiome and modify the known effects of emollient on skin microbiome and barrier protection, though the direction of the effect is difficult to hypothesize.

In addition, **subgroup analyses by sex/gender and race and/or ethnicity** are required under the Inclusion of Women and Minorities policy of the NIH (NOT-OD-18-014). Coding for these variables will be as follows:

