5.5. Exploratory Subgroup Analyses

In exploratory analyses we will investigate potential differences in treatment effect in subgroups with known or hypothesized risk or protective associations with AD. These are defined in the "Definitions for Subpopulation Analyses" section above.

For each analysis, we will estimate differences in the treatment effect on both the absolute (i.e. risk difference) and relative (i.e. ratio) scales. After calculating the raw differences, we will estimate them based on a model that incorporates the same variables as in other analyses, but with main effects and interactions for the subgroup variables outlined above. Most of these are either binary or continuous; in the case of a multi-level categorical variable, we will use a set of design variables. The analysis addressing ceramides will only use main effects, without interaction terms. The model will use the full ITT dataset with provider-diagnosed AD as the outcome. The p value for the single interaction coefficient (or for the combination of interaction coefficients, if multiple design variables are used) will provide an estimate of statistical significance for a difference in treatment effects in the subgroups being modelled. We plan to use a significance threshold of 0.10 for identifying effects that may warrant further investigation. (Designing the trial for a lower threshold was not feasible.)

More important than p values, we plan to rely on the magnitude of effects to determine whether the intervention is more effective in some subgroups than others. It is difficult to specify a threshold for the magnitude of difference in advance. The planned presentation of results is given in Table 5.

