5.7. Analysis of Effect of Reported Emollient Use

Because the intervention uses an accessible, non-prescription topical emollient, either study arm might have users and non-users (compliant/non-compliant with study assignment). In the spirit of a *per-protocol analysis*, similar to the main analysis, we will classify participants by their reported emollient use (>weekly, on average, for the time up to diagnosis or end of follow-up) rather than assigned intervention arm. Under this coding, some participants assigned to the treatment arm might be non-users, and others assigned to the control arm may report regular emollient use; those individuals would be in different groups than under the main analysis, which uses assigned treatment arm.

Parent-reported frequency of emollient use (in days per week) will be summarized for the intervention and control arms for each quarterly follow-up time point from age 3 to 24 months (8 quarters). In this analysis, we will exclude observations after a diagnosis of AD, because emollient use is likely to reflect treatment rather than prevention. For example, if a parent reports a diagnosis of AD on the 9-month contact, that child's emollient use at 3 and 6 months will be included, but not 9 months or later. All of the definitions of AD diagnosis will be considered, i.e. GS-AD, PR-AD, CEQ-AD, etc. For missing responses, we will carry the last observation forward. Distributions over time will be graphed.

The relationship between frequency of emollient use and AD will be tested using a variable that is the average of each individual's frequency responses. We hypothesize that the intervention will increase the frequency of emollient use, and that more frequent emollient use will be associated with lower incidence of AD. If this is true, we expect that frequency will be associated with study arm (using a two-sample t-test or Wilcoxon rank-sum test, if skewed), that study arm will be associated with prevalence of AD (primary analysis), that higher frequency of emollient use will be associated with lower prevalence of AD (Equation 1 with emollient frequency substituted for study arm), and that including both treatment arm and emollient frequency in a model with AD as the outcome will change the estimate of treatment effect, which will be taken as evidence that frequency of emollient use is in the causal pathway.

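### The exploratory ceramide comparison counts CeraVe use at any time, with no cut-off at AD, so switches made after AD appears can decide which product group a child falls in

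*SAP*

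**What the plan says.** SAP section 5.2, item 4 defines the ceramide comparison as CeraVe "cream or ointment (at any time) vs all other emollients in the treatment arm vs controls". The design variables are "ceramides (1=CeraVe cream or ointment, 0=otherwise) and other emollients in the treatment arm (1=used, 0=not used"), with controls as the reference group. The SAP does not say whether the CeraVe indicator comes from product assigned, shipped or reported as used, or that the two indicators exclude each other.

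SAP section 5.5 gives the model: "The model will use the full ITT dataset with provider-diagnosed AD as the outcome", and "The analysis addressing ceramides will only use main effects, without interaction terms". It adds that the size of effects will count for more than p values.

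On product changes, protocol section 5.1 tells parents that "they can change emollients at any point during study participation", provided the new product is on the approved list. Under protocol section 5.2, intervention families "will receive a six-month supply of emollient at enrollment, 6 months, 12 months, and 18 months", and the contacts in section 6.2 reconfirm the preferred product at 6, 12 and 18 months. Section 4.7.1 states that infants who develop AD are not withdrawn.

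SAP section 5.7, which analyses frequency of emollient use, drops use reported after an AD diagnosis "because emollient use is likely to reflect treatment rather than prevention". SAP Table 4 likewise restricts its frequent-user variable to time points before diagnosis. Neither restriction is carried into item 4.

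For families that do not choose a product within three business days of enrollment, protocol section 5.2 says: "The dyad will be assigned CeraVe cream, the most popular emollient".

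**The concern.** Exposure should be settled before the outcome, or at least not by it. Here it need not be. A rash is a plausible reason to try a different product, and a first CeraVe jar sent after the rash appeared still puts the child in the CeraVe group, bringing the AD diagnosis along.

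The rule also works in one direction. Moving to CeraVe adds a child to the group, while moving away never removes one, so two-way switching does not cancel the error.

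The comparison was added because of emerging evidence on ceramides, so readers will look at it. Section 5.5 tells them to weigh the magnitude of the estimate, and magnitude is what this rule distorts. A larger sample would not help.

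**Working it through.** **The plan's own figures.** The SAP gives no number for the ceramide comparison. It does give the AD risks used below: 24% in controls and 0.70 × 24% = 16.8% under the intervention (SAP section 2.3). Its 491 per arm for that difference reproduces (two proportions, two-sided 0.05, 80% power, pooled variance, no continuity correction). The ceramide point does not depend on the sample size.

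**Assumptions, none of them in the documents**
- c = share of intervention families on CeraVe at baseline: 40%.
- s0 = chance that a non-case on another product switches to CeraVe: 10%.
- s1 = the same chance for a case: varied.
- p = AD risk, the same on every product: 16.8%. The true CeraVe/other RR is therefore 1.00.
- Groups are mutually exclusive (CeraVe ever, or never).

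**Formulae**, as fractions of the intervention arm:
- CeraVe cases = p × [c + (1 − c) × s1]
- CeraVe non-cases = (1 − p) × [c + (1 − c) × s0]
- Other cases = p × (1 − c) × (1 − s1)
- Other non-cases = (1 − p) × (1 − c) × (1 − s0)

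**Worked case, s1 = 20%**
- CeraVe cases = 0.168 × 0.52 = 0.0874; non-cases = 0.832 × 0.46 = 0.3827; risk = 0.0874 / 0.4701 = 18.6%.
- Other cases = 0.168 × 0.48 = 0.0806; non-cases = 0.832 × 0.54 = 0.4493; risk = 0.0806 / 0.5299 = 15.2%.
- Apparent RR = 1.22.

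**Range of s1** (ratios from unrounded risks; the last column repeats the calculation with c = 70%)

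| Cases switching (s1) | CeraVe risk | Other risk | RR, c = 40% | RR, c = 70% |
|---|---|---|---|---|
| 5% | 15.9% | 17.6% | 0.90 | 0.94 |
| 10% (same as non-cases) | 16.8% | 16.8% | 1.00 | 1.00 |
| 20% | 18.6% | 15.2% | 1.22 | 1.14 |
| 30% | 20.3% | 13.6% | 1.50 | 1.32 |
| 40% | 21.9% | 11.9% | 1.85 | 1.56 |

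Both comparisons with control move as well. At s1 = 30% and c = 40%, CeraVe versus control is 20.3 / 24 = 0.85 and other products versus control is 13.6 / 24 = 0.57, when both are truly 0.70.

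**Significance at the planned 0.10 level.** This was simulated with 20,000 replicates of 491 intervention infants, c = 50%, s0 = 10% and no ceramide effect, using a two-proportion test. The any-time rule rejects in 21%, 51% and 97% of trials at s1 = 20%, 30% and 50%. Grouping by baseline product rejects in about 10%, as it should.

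**Would a fixed indicator of use before diagnosis cure it?** No. Non-cases have the whole follow-up in which to become CeraVe users, while cases have only the time until diagnosis, so cases would be expected to show fewer counted switches. If 5% of cases and 10% of non-cases have a counted switch, the first row applies: RR 0.90 with no true effect. This is immortal-time bias in favour of CeraVe. Section 5.7 averages a frequency over the pre-diagnosis contacts, so its exclusion cannot simply be copied to an ever-used indicator.

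**The case against.** The strongest objection is that the size rests entirely on assumed switching rates. This stands. The documents give neither those rates nor the CeraVe share. If switching to CeraVe is unrelated to AD, the RR is 1.00, and if cases switch less often than non-cases, the error reverses. The protocol calls CeraVe cream the most popular choice, and a larger share shrinks the bias, as the last column of the table shows. The calculation also assumes exclusive groups. If a switcher scores 1 on both indicators, the planned model estimates something else.

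A second objection is that the analysis is exploratory, declared unpowered and based on self-selected products, so it is non-randomised under any definition. This limits the weight of the point but does not answer it, because section 5.5 relies on magnitude. Table 4 already plans to report baseline choice, final choice and whether the family switched. That would show how much switching occurred but would not correct the estimate.

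A reader might also infer that default assignment to CeraVe makes the groups outcome-dependent. The documents do not support that. The default is set within days of enrollment, in infants without diagnosed eczema by parent report, so it precedes the outcome. It raises a different question: whether these families differ in engagement or actual use. Even that they count as CeraVe users is an inference, since the data source is not stated. If 10% to 50% of the CeraVe group were default families who applied nothing (risk 24%), the CeraVe/other RR would be 1.04 to 1.21. For 10%, this is (0.9 × 16.8 + 0.1 × 24) / 16.8 = 1.04. That is dilution, not reverse causation.

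**Conclusion.** The exposure rule is unsafe as written. Followed literally, it lets a switch made after AD decide group membership, and the safeguard in section 5.7 does not reach it. This is a flaw in a stated rule rather than a missing detail.

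The size and direction of the bias cannot be determined from the documents. The illustrative RRs of 0.90 to 1.85 against a truth of 1.00 depend on the assumed 40% baseline share, the 10% switching rate in non-cases and the range of rates in cases. A reader might infer that CeraVe will be made to look harmful. That follows only if cases switch to it more often than non-cases, which is plausible but not documented.

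The point concerns one exploratory, non-randomised comparison. The primary analysis uses assigned arm and is untouched.

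**What to change.** In SAP section 5.2, item 4:

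1. Define the product groups by the first emollient selected or shipped at randomisation, and state the data source. Table 4 already lists baseline emollient choice, and protocol section 5.6 has brand and shipping date logged by participant.
2. Make the CeraVe and other-emollient indicators mutually exclusive, to match the separate rows for CeraVe, others and none in Table 5.
3. If later use is also analysed, treat product as a time-varying exposure up to AD diagnosis, not as a fixed indicator of any use before diagnosis.
4. As a separate matter, flag families assigned CeraVe cream by default and leave them out in a sensitivity analysis, because they may differ in engagement.

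The first two changes need a few lines of SAP wording and no new data. The cost is that genuine later switches are not credited in the main version, and the question becomes initial product choice rather than any use. A time-varying analysis, if wanted, is extra modelling work. The comparison stays exploratory and non-randomised.

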2.3. Sample Size and Recruitment Duration

1,250 parent/infant dyads (625 per arm) will be enrolled from 25 community-based family medicine and pediatric practices in four states (Oregon, Colorado, Wisconsin, and North Carolina). All parents/legal guardians, including males and females 18 years of age and older who meet inclusion/exclusion criteria are eligible for study participation. Recruitment is expected to take place over the course of 31 months; the time from start of recruitment until final two-year follow-up on all subjects is five years.

Power for Aim 1. For the purpose of the primary analysis, we include a sufficient number of babies in a 1:1 ratio for the two study arms to provide an overall type I error rate of 0.05 and 80% power to detect a 30% relative reduction in cumulative incidence of AD by two years of age (RR=0.7). In our planning grant, we determined the baseline cumulative incidence of AD in this age group and target clinics at 24%, which is consistent with recent population-based 2-year prevalence in the U.K.¹. Because our trials in high-risk populations of daily vs no emollient have shown reductions of 50%, we assume a more conservative 30% reduction to 16.8%. Using a test of two proportions, a total of 982 babies (491 per arm) are required to detect this difference. Allowing for an approximate 20%

¹ The screening questionnaire includes the question "Has at least one of your baby's blood-related PARENTS, BROTHERS OR SISTERS ever been diagnosed with asthma, eczema (atopic dermatitis) or hay fever (seasonal allergies)?" Strata are split at "Yes" responses vs. "No, or don't know."

loss to follow-up, we plan to enroll 1,250 babies (625 per arm). Sample size calculations were performed using Stata/IC version 16.1.

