3.1. Level of Statistical Significance

In the primary analysis, use a type I error rate of 0.05. Secondary outcomes will be considered significant at $\alpha=0.05$ and exploratory analyses at $\alpha=0.1$. All tests will be two-tailed.

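### The exploratory ceramide analysis compares each product group with controls and names no test of CeraVe against the other emollients, which is the comparison its motive calls for

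*SAP*

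**What the plan says.** SAP 5.2 item 4 gives its reason for looking at CeraVe: a recent study suggested that "previously observed benefits from regular emollient use may be attributable to ceramides". It then limits expectations: "Although we are not powered to detect a significant difference from ceramide-containing emollients versus others". The aim it goes on to state is milder, namely to see whether use of the ceramide products goes with less AD.

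The model is set out in three statements:

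- "The planned design variables for this analysis are for ceramides (1=CeraVe cream or ointment, 0=otherwise", with a second indicator for other emollients in the treatment arm (SAP 5.2 item 4).
- "Controls will be used as the reference group" (SAP 5.2 item 4).
- "The analysis addressing ceramides will only use main effects, without interaction terms" (SAP 5.5).

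For the other subgroup analyses, SAP 5.5 takes the p value for a difference in effect from the interaction coefficient. On the threshold it says: "We plan to use a significance threshold of 0.10 for identifying effects that may warrant further investigation". It also ranks magnitude of effect above p values. Table 5 has rows for CeraVe, other emollients and none, with columns for differences on both scales and for an interaction p value.

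**The concern.** A claim about ceramides is a claim that ceramide products do better than other emollients. In the planned model the CeraVe coefficient is the log RR of CeraVe users against controls, so its null is that CeraVe users have the control risk. If every emollient works equally well, that null is false and the coefficient will often be significant, although ceramides add nothing.

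SAP 5.5 removes the interaction term for this analysis and names no replacement, so the plan does not say what goes in the interaction p value cell of Table 5. The only p values the specified model gives directly are the two comparisons with controls. CeraVe users may well be the larger group: CeraVe supplies two of the five products, and Protocol 5.2 makes CeraVe cream the default and calls it the most popular. CeraVe could then be significant, and the others not, because of group size alone.

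A second issue is coding. CeraVe use counts if it happened at any point, and Protocol 5.1 lets parents switch. The SAP does not say whether a family that used both types scores 1 on both indicators.

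**Working it through.** **Inputs.** From SAP 2.3: control risk 24%, planned RR 0.70 (16.8%), and 625 per arm less about 20%, so 625 × 0.8 = 500 evaluable per arm. From SAP 5.5: alpha 0.10. From SAP 3.1: "All tests will be two-tailed". Assumption: the CeraVe share of the treatment arm is not in the documents, so I use 40–80%.

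**The plan's own figure.** The trial is sized "to provide an overall type I error rate of 0.05 and 80% power". With pooled variance and mean risk 0.204:

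n per arm = [1.96√(2 × 0.204 × 0.796) + 0.8416√(0.24 × 0.76 + 0.168 × 0.832)]² / 0.072² = (1.117 + 0.478)² / 0.005184 ≈ 491.

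This is 982 in total, as stated. The documents give no power figure for the ceramide analysis.

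**CeraVe versus controls when all emollients are equal.** For two groups, SE(log RR) = √[(1−p₁)/(n₁p₁) + (1−p₀)/(n₀p₀)]. At a 60% share there are 300 CeraVe users and 500 controls:

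- SE = √(0.832/50.4 + 0.76/120) = 0.151.
- |ln 0.70| / SE = 0.357/0.151 = 2.36.
- Probability of significance = Φ(2.36 − 1.645) ≈ 0.76.

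**Simulation.** AD counts were binomial, with Wald tests on log RR, two-sided 0.10, exclusive product groups and a common RR of 0.70. Family history, the clinic effect and imputation were left out.

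| CeraVe share | CeraVe vs control significant | CeraVe only | Others only | Both | Direct contrast rejects |
|---|---|---|---|---|---|
| 40% | 67% | 11% | 22% | 56% | 10% |
| 50% | 74% | 16% | 15% | 58% | 10% |
| 60% | 78% | 22% | 11% | 56% | 10% |
| 70% | 82% | 31% | 7% | 50% | 10% |
| 80% | 84% | 44% | 4% | 40% | 10% |

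Over the same shares, the CeraVe coefficient is significant in 38–53% of trials at a common RR of 0.80 and in 17–22% at 0.90. A separate run with family history in a robust Poisson model (491 per arm, RR 0.70) gave 68%, 78% and 81% at shares of 40%, 60% and 70%, with the contrast at 10–11%.

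**The direct contrast.** If only ceramide products work (RR 0.70 versus 1.0), at a 60% share SE = √(0.832/50.4 + 0.76/48) = 0.180. Power is then Φ(0.357/0.180 − 1.645) ≈ 0.63. Across shares of 40–70% it is about 60–63%.

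**Families who used both types.** Suppose 20% of the arm scores 1 on both indicators and the true RR is 0.70 for everyone. A main-effects log model makes the dual users' RR the product of the two coefficients, 0.70 × 0.70 = 0.49 if both were right. The fit has to compromise. With 40% CeraVe only and 40% other only, both coefficients settle at about 0.77. With 50/30 or 30/50 they are about 0.76 and 0.79. Both are pulled toward 1, while dual users are fitted at about 0.60.

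**The case against.** The strongest reply is that the model answers the question the SAP finally asks. It disclaims power for ceramides against other emollients and then asks only whether CeraVe use goes with less AD. For that, CeraVe against controls is a proper test. This stands.

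A reader might take 67–84% beside a 10% level as a badly inflated false-positive rate. It is not. In those scenarios CeraVe does reduce AD, so rejecting is correct; the figures are power against a null that is false. The error arises only if the p value is then read as evidence about ceramides, and the SAP does not say it will be.

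A reader might also infer that any general emollient effect would be credited to ceramides. The documents do not support that. The same model estimates the other-emollient effect, Table 5 sets the groups side by side with difference columns, and SAP 5.5 puts magnitude first. With equal emollients at RR 0.70, both coefficients being significant is the most frequent pattern at shares of 40–70%. At a 50% share the two one-sided patterns are about equally likely.

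Finally, overlapping indicators are only one reading. The item's title and the three rows of Table 5 can also be read as exclusive groups.

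What remains is that neither SAP 5.2, SAP 5.5 nor Table 5 names a CeraVe-versus-others test, interval or p value, although the motive is specific to ceramides. Disclosing low power does not tell a reader that the specified coefficients address a different comparison.

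**Conclusion.** The point holds as a gap between motive and test, not as a faulty test. The CeraVe-versus-control coefficient validly shows whether CeraVe users have less AD than controls, but cannot show that ceramides are the reason. At the SAP's own RR of 0.70 it would usually be significant with no ceramide effect at all; at a common RR of 0.80 this is roughly an even chance or less, and at 0.90 it is uncommon. The sizes rest on 500 evaluable per arm, 24% control risk, exclusive groups and an assumed CeraVe share of 40–80%. The misleading pattern of CeraVe significant and others not ranges from 11% to 44% with that share. The coding bias applies only if dual users score 1 on both indicators.

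The analysis is exploratory and the primary result is untouched.

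**What to change.** In SAP 5.2 item 4, SAP 5.5 and Table 5:

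- Make the ceramide estimate the contrast, CeraVe coefficient minus other-emollient coefficient, from the same model. Report it as an RR with 90% CI, and put its p value in the Table 5 cell now headed for interaction.
- Use mutually exclusive categories: CeraVe only, other only, both.
- Label the two RRs against controls as emollient effects among users of each product type, and state that they do not test a ceramide effect.
- Describe the contrast as an association, because parents chose the product and it was not randomised.

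The cost is a few sentences and one linear combination, with no new data. The downside is lower precision. At a 60% share and common RR 0.70 the contrast has SE √(0.832/50.4 + 0.832/33.6) = 0.203, against 0.151 for CeraVe versus controls. A separate category for dual users would widen it further.
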